4.1 Hypothesis

Myoelectric signaling patterns of the abdominal cavity after surgery will correlate with first flatus.

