4.2 Primary Objective

To measure myoelectric signals with the G-Tech WPS and determine if a correlation exists between signal strength and the rate of gastrointestinal recovery following colorectal surgery. Determine the relationship between gastrointestinal myoelectrical signal strength and clinical markers of recovery such as passage of flatus/bowel movement, oral tolerance of diet, and discharge readiness.

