5.2 Outcome Variables

5.2.1 Primary Outcome Variables

GI functional recovery after surgery as measured by first flatus

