6.4.3 Planned Analysis

6.4.3.1 Primary Analyses

The primary endpoint is to determine if there is a correlation between the measured motor activity metrics of the various GI organs with measures of recovery, and to mathematically characterize the correlation in a manner that leads to predictive ability. The study is retrospective without intention to treat. Data analysis is performed by the staff of G-Tech Medical located in Mountain View, CA using proprietary software developed specifically for this purpose. Data is accessed on a secure cloud server to which it was uploaded by the mobile app connected to the patches.

Data analysis consists of extracting the myoelectric motor activity measured by the patches in ten-minute time segments and assigning them to an organ or organs. The motor activity at any one time (instantaneous) and the cumulative activity up to that point in time will be examined for correlation to parameters associated with recovery rate such as time to first flatus, time to first solid meal, time to discharge, etc. This will be done across all time points to find the earliest time that offers predictive value. The specific final analysis approach taken will depend on the findings of this pilot study.

In the study² with colonic myoelectric activity measurements after open abdominal surgery an inverse correlation was found between cumulative colon signal strength and time to first flatus which was approximately linear and was best characterized by the root mean square (RMS) deviation of the residuals from a linear fit, in units of hours. The optimal time for this analysis was found to be at 36 hours after surgery.

Similarly in the study¹ with patients undergoing pancreaticoduodenectomy procedure, a correlation was found between cumulative signal strength of the stomach and time to first full meal that was also inverse but not well represented by a linear or other fit. In this case the analysis involved assigning patients to one of two groups, early and late feeders. The stomach activity data were then tested for predictive value against these groups. Patients with stronger signals were more likely to be in the early feeding group and vice versa. A statistical analysis was performed using a receiver-operator characteristic approach that led

pancreaticoduodenectomy for diet “readiness”. American Journal of Physiology-Gastrointestinal and Liver Physiology, 315(5), pp.G743-G751.

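### First flatus is the primary outcome, but the primary analysis gives it no single prespecified test and takes an earliest predictive time from an uncorrected search in the same patients

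*Combined protocol and SAP*

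**What the plan says.** Section 4.1 states the hypothesis: "Myoelectric signaling patterns of the abdominal cavity after surgery will correlate with first flatus". Section 5.2.1 names one primary outcome: "GI functional recovery after surgery as measured by first flatus". Section 4.2 is broader and covers "clinical markers of recovery such as passage of flatus/bowel movement, oral tolerance of diet, and discharge readiness".

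Section 6.4.3.1, headed Primary Analyses, describes the data step as "extracting the myoelectric motor activity measured by the patches in ten-minute time segments and assigning them to an organ or organs". It continues: "The motor activity at any one time (instantaneous) and the cumulative activity up to that point in time will be examined for correlation". The recovery measures are an open list: flatus comes first, then the first solid meal, discharge and others not named. The selection rule is "This will be done across all time points to find the earliest time that offers predictive value", and the section adds: "The specific final analysis approach taken will depend on the findings of this pilot study".

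The same section reports two earlier studies. One related cumulative colonic activity to flatus by a linear fit, summarised by the RMS residual in hours: "The optimal time for this analysis was found to be at 36 hours after surgery". The other used a receiver-operating-characteristic (ROC) approach for stomach activity and feeding. Both are told as history, and neither is adopted as this study's test.

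Sections 6.4.1 to 6.4.5 contain no fixed test for flatus, no alpha, no definition of predictive value, no adjustment for the search and no validation or resampling step. Section 6.4.3.2 only adds further correlations (ileus, readmission, first bowel movement).

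**The concern.** The plan has a hypothesis about one outcome and an analysis that searches over several outcomes, organs, metrics and times. Its rule picks the earliest look that seems to work and judges it in the patients who supplied the look.

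Two biases follow. With many correlated looks, the first to cross any bar tends to come before the relation really begins. Accuracy at a look chosen for its accuracy is also flattered. The study would then report a time and a performance figure that a new sample would probably not reproduce, and it would have no single result that answers section 4.1.

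**Working it through.** **Plan's own figure.** There is no error rate to reproduce. The 200 in section 6.4.2 cannot be rebuilt either, because no alpha, power or effect size is given.

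**Size of the search.** Ten-minute segments give 36 × 6 = 216 looks by 36 h. Scanning from 6 to 36 h gives (36 − 6) × 6 = 180 steps per series. With 2 metrics and 2 or 3 organs, that is 180 × 2 × 2 = 720 or 180 × 2 × 3 = 1,080 correlations for flatus alone. They are strongly correlated, so an independence formula does not apply and simulation is needed.

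**Inputs from the documents.** n = 200 (5.3.1); ten-minute grid and two metrics (6.4.3.1); patches on within 4 h (6.1.2).

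**Inputs assumed.** Flatus only; 2 or 3 organs; ten-minute autocorrelation 0.9, 0.97 or 0.995; stable between-patient share of variance 0.2, 0.5 or 0.8; organ correlation 0.2 or 0.8. That makes 2 × 3 × 3 × 2 = 36 settings, with 400 runs each. The per-look threshold is also assumed.

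**Critical value.** |r| = t/√(n − 2 + t²). At two-sided 0.05, 1.972/√(198 + 3.889) = 0.139. It is 0.182 at 0.01 and 0.231 at 0.001.

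**Chance of at least one false positive, no true relation:**

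| Rule | Range | Median |
|---|---|---|
| Full scan, 0.05 per look | 19–100% | 55% |
| Full scan, 0.01 per look | 6–81% | 19% |
| Full scan, 0.001 per look | 0–22% | 4% |
| One organ, cumulative only, 0.05 per look | 5–18% | 10% |
| One fixed 36-h test, 0.05 | 3–7% | 5% |

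Outside these settings, with no stable patient differences and a scan from 4 h, the one-organ cumulative figure is 23% at autocorrelation 0.97 and 27% at 0.9. At 0.5, two separate simulations gave 37% and 45%.

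A maximum-statistic permutation test with skewed flatus times (5 settings, 400 runs, 99 permutations) rejected in 3–5.5% of null runs, against 16–100% unadjusted.

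**Earliest time.** Let a true relation start at 24 h and ramp to an instantaneous r of 0.3 or 0.4 at 36 h (24 settings, 300 runs each). At 0.05 per look, the scan puts the earliest time at or before 24 h in 17–97% of runs. With the maximum-statistic threshold this is 1–7%, the median earliest time is 29.0–32.8 h, and detection by 36 h is 88–100%.

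**Accuracy when the truth is chance** (16 settings, 80 runs each). The in-sample area under the ROC curve (AUC) for early versus late flatus is 0.56–0.62 at the best look and 0.56–0.57 at the earliest look passing 0.05. Five-fold cross-validation with the selection repeated gives 0.495–0.508.

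**RMS.** The optimism is 1 − √(1 − r²), with r the largest chance correlation. It averages 0.6–2.3% for the scan and 0.3–0.6% for one organ's cumulative activity. On the ±22 h in section 2.1.2 the scan figure is 22 × 0.006 = 0.13 h to 22 × 0.023 = 0.51 h.

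**Power of a fixed test.** Detectable |r| at 80% power is tanh((1.960 + 0.842)/√(n − 3)): 0.197 at n = 200, 0.227 at 150, 0.277 at 100 and 0.355 at 60.

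**Power of the adjusted scan.** The scan-adjusted critical |r| is about 0.17–0.27. Power at r = 0.3 is Φ((atanh 0.3 − atanh r_crit) × √197):
- r_crit 0.139: (0.3095 − 0.1399) × 14.04 = 2.38, so 99%.
- r_crit 0.17: (0.3095 − 0.1717) × 14.04 = 1.93, so 97%.
- r_crit 0.27: (0.3095 − 0.2769) × 14.04 = 0.46, so 68%.

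**The case against.** The study calls itself feasibility, pilot and Phase 1 (5.1, 6.4.3.1, 3.2) and openly leaves the final method to its findings, so its exploratory status is largely declared. That stands as a defence of the scan. It does not cover placing the scan under Primary Analyses, unlabelled, beside a stated hypothesis and a single primary outcome, when an earlier study already offers a fixed candidate time.

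The plan never says that a look counts at p < 0.05, so the large error rates test a rule supplied from outside. This stands: they are illustrations, and a strict threshold shrinks them a great deal. But the plan supplies no threshold at all, strict or loose.

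For flatus, the only metric described is RMS, where the optimism is trivial. This also stands. The AUC figures apply only if the ROC approach, described for stomach activity and feeding, is carried over to flatus.

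A reader might infer more than the documents support:
- That flatus is never analysed. It is listed first among the recovery measures; what is missing is one prespecified test.
- That section 4.2 contradicts 5.2.1. It is broader, but flatus is in both.
- That the manufacturer tunes its method to outcomes as they arrive, since signals and event times share its server (7.6) and analysis overlaps collection (5.1.1). Section 5.1.1 ties the overlap to algorithmic processing, which may mean the signals alone, and 6.4.3.5 plans no interim analysis.
- That the selected time will steer feeding decisions. Section 3.2 speaks only of later study of the data, and 7.12 says that the treating team does not receive the information.

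**Conclusion.** The point holds in this limited form: the primary outcome lacks a prespecified primary test, and an uncorrected earliest-time rule takes its place. No figure in the plan is shown to be wrong. The direction of the bias follows from the rule as written. Its size depends on autocorrelation, organ count and a per-look threshold, none of which the documents give. It ranges from modest for one organ's cumulative activity in the main settings to near certainty of a false positive in the widest search. The bias matters for the selected time and for classification accuracy, and hardly at all for RMS. Confidence is high on the text and moderate on the magnitudes. This is a cheap improvement worth making, not a threat to patients or to the feasibility aim.

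**What to change.** Amend section 6.4.3.1:

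1. Name one primary test for time to first flatus, with its organ, metric, time and alpha. An example is cumulative colonic activity at 36 h, two-sided 0.05. That time was itself the optimum in an earlier study of open abdominal surgery, and this study also takes laparoscopic resections, so its transfer is an assumption. State how patients with flatus before that time are handled, for example by a landmark analysis that reports the number remaining.
2. Label all other times, organs, metrics and outcomes exploratory. Adjust their p-values and the earliest time by permuting outcomes and rerunning the whole scan (maximum statistic).
3. Report RMS, sensitivity, specificity or AUC at a selected time only from cross-validation that repeats the choice of time, organ and metric in each fold.

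Optional: align section 4.2 with 5.2.1, and date the primary test before outcomes are analysed.

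The cost is wording and computing time, with no new patients. Accuracy figures will look less favourable and the adjusted earliest time will be later, because it is conservative. Exploratory power at r = 0.3 falls from 99% to about 97–68%. The fixed test's detectable |r| of about 0.20 at n = 200 is a best case. It rises once the landmark and the exclusions in 6.3.7 and 6.4.5 remove patients, whose number the documents do not give.

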6.4.3.2 Secondary Objectives Analyses

In addition to the analysis above, electronic medical record review will allow for the rate of ileus, readmission, and first bowel movement to be further correlated with the processed myoelectric signal.

6.4.3.3 Safety

Anticipated and unanticipated adverse device events will be monitor through hospitalization and 30-days after surgery based on the definitions above. Descriptive statistics will be reviewed with the study team and the manufacturer.

6.4.3.4 Analysis of Subject Characteristics

Descriptive statistics will be reported for age, sex, race, indication for surgery, type of anatomic resection, ostomy present preoperatively, ostomy present postoperatively, duration of operation, operative approach (open, laparoscopic, robotic).

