2.2 Background/prevalence of research topic

Gastrointestinal recovery after any visceral surgery is a complex dynamic process with multiple factors ranging from complexity of the surgery, degree of bowel handling and preoperative comorbidities affecting whether the recovery happens over few days, or is a slow prolonged affair lasting weeks.¹ Delays in the gastrointestinal recovery process or ileus is accompanied by distention of the abdomen, pain, nausea, vomiting and the inability to tolerate oral feeding.^{2,3} Interventions to alleviate the ileus/distention include insertion or reinsertion of a nasogastric tube, instating *nil per os* and, if necessitated, parenteral

nutrition.⁴ All of these factors contribute not only to patient discomfort, but extend length of stay (LOS), increase hospital resource utilization and thereby add to overall costs.⁵⁻⁷

Clinically, the markers of gastrointestinal recovery are noted by passage of flatus, defecation and the ability to tolerate solid food without significant nausea and vomiting.⁸ Passage of stool or flatus - considered a surrogate for intestinal and anastomotic continuity - is often used as the trigger to start stepwise dietary orders with the patient's ability to tolerate each step marking their readiness for the subsequent meal. Fast-track and Enhanced Recovery After Surgery (ERAS) programs that promote early feeding in advance of these clinical markers, along with opioid sparing techniques and use of minimally invasive procedures have been shown to be safe and beneficial for many patients by demonstrating earlier recovery and shorter length of stay.⁹⁻¹¹ However, it has also been shown that, for as many as 25% of cases, the strategy does not work as noted earlier, with the need for reinsertion of the nasogastric tube and reinstating nil per os status. In a recent study of 513 consecutive colorectal patients who were on an ERAS protocol, 128 patients (24.7%) needed postoperative reinsertion of nasogastric tube at the 3.9 ± 2.9 postoperative day.⁹ This suggests that, while early postoperative feeding is beneficial to patients in whom recovery is on track, it does not work in cases where patients are not ready for it.

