5.3.2 Eligibility Criteria/Vulnerable Populations

Any subject who undergoes an open or laparoscopic colon or rectum resection surgery

Inclusion Criteria:

1. Willing and able to provide informed consent
2. Eighteen (18) years of age or older
3. Subject is willing and able to follow all study requirements
4. Subject has undergone or will undergo a laparoscopic or open colorectal surgery with resection and anastomosis

Exclusion Criteria:

[figure not shown]
1. Subject is pregnant or suspects pregnancy.
2. Known allergy to medical grade adhesive.

6 Methods

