6.4.4 Subsets and Covariates

See subject characteristics above 6.4.3.4.

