Patient ID # _____

Planned Surgery (pick one)

Enterectomy Only

Right-sided Colectomy

Left-sided Colectomy

Proctectomy

Date of Planned Surgery ___/___/___

ELIGIBILITY

1. Inclusion Criteria (All responses must be “YES” below)

	YES	NO
a. Subject is willing and able to provide informed consent;		
b. Subject is ≥ 18 years of age;		
c. Subject is willing and able to follow all study requirements;		
d. Subject who will undergo or has undergone open or laparoscopic colorectal surgery		

2. Exclusion Criteria (All responses must be “NO” below)

	YES	NO
a. Subject has a known allergy to skin adhesives;		
b. Subject is pregnant or suspects pregnancy;		

2. Informed Consent Obtained

a. Informed Consent Obtained

Y N

2000032548

4/19/22 v1.3

b. Date of Informed Consent ____/____/____

1. Demographics

1. Date of Birth	____	____	/	____	____	/	____	____	____	
	MM	DD		YYYY						
2. Gender		Male		Female						
3. Stated Height	____	Feet	____	Inches						
4. Stated Weight	____	____	____	lbs.						
5. Ethnicity		Caucasian		Black		Hispanic		Asian		Other:

Appendix 3

Recording Procedure and Clinical Markers Case Report Form

Patient ID # _____

Date of Surgery ____ / ____ / ____

Procedure Performed (pick one)

Enterectomy Only

Ostomy Preop? Y N

Right-sided Colectomy

Ostomy post? Y N

Left-sided Colectomy

Proctectomy

POSTOPERATIVE MARKERS

First Flatus Date ____ / ____ / ____

First BM Date ____ / ____ / ____

First Solid Food ____ / ____ / ____

Clinical Ileus (emesis after POD 2, no flatus, reversal of diet order, +/- NGT placed)

Y N

Readmission Y N

Reason for Readmission (choose any)

[] Ileus

[] Dehydration

[] Infection / Anastomotic Leak

[] VTE

[] Unknown

[] Other:

Readmission likely related to surgery? Y N

Appendix 4

Protocol Deviation Form

Date(s) Deviation Occurred:

(If this deviation occurred over multiple days, please indicate entire deviation period)**Associated Study Visit (if applicable):****Type of Deviation**

- Informed consent not properly obtained

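### Patients with an anastomosis and a postoperative ostomy are expected, but flatus and bowel movement are recorded without route and no rule separates these patients, so one pooled correlation can be distorted

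*Combined protocol and SAP*

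**What the plan says.** Section 5.2.1 defines the primary outcome as "GI functional recovery after surgery as measured by first flatus". Section 5.2.2 adds first bowel movement as a secondary outcome. Neither mentions a stoma.

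The surgical inclusion criterion in 5.3.2 is "Subject has undergone or will undergo a laparoscopic or open colorectal surgery with resection and anastomosis". The only exclusions are pregnancy and adhesive allergy. The eligibility checklist in Appendix 2 is looser and asks for neither a resection nor an anastomosis.

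Ostomy patients are foreseen. The clinical markers form in Appendix 3 has the field "Ostomy post? Y N", and 6.4.3.4 includes "ostomy present preoperatively, ostomy present postoperatively" in its descriptive list. Appendix 3 has one date for first flatus and one for first bowel movement, with no field for route or stoma type.

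The primary analysis in 6.4.3.1 relates motor activity to "parameters associated with recovery rate such as time to first flatus, time to first solid meal, time to discharge, etc", over all time points, and adds: "The specific final analysis approach taken will depend on the findings of this pilot study". It names no exclusion, stratum or adjustment for ostomy. The whole of 6.4.4, on subsets and covariates, is "See subject characteristics above 6.4.3.4".

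The rationale in 2.2 gives flatus a specific meaning: "Passage of stool or flatus - considered a surrogate for intestinal and anastomotic continuity".

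**The concern.** In a patient who has both an anastomosis and a stoma, the stoma would ordinarily lie upstream of the join. That is a clinical assumption, because the documents do not describe stoma types. First gas or output then appears in the appliance without having crossed the anastomosis. By the protocol's own reasoning in 2.2, this is a different event from flatus in a patient without a stoma, yet both go into the same field under the same name.

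The hypothesis in 4.1 is that the signal correlates with first flatus, and 6.4.3.1 aims to turn that correlation into a prediction. If two kinds of event are combined, the coefficient, the prediction error and the time point chosen as best may describe neither group well. First bowel movement has the same problem.

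**Working it through.** **1. Is pooling the likely default?** Set side by side, the sections suggest so:

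- 6.4.3.1: the manufacturer's staff run the analysis on data uploaded by the app.
- 7.5: the minimum entries in the app are the times of first flatus, first bowel movement, first solid meal and discharge. Ostomy status is not among them.
- 7.6 and 7.7: clinical history and the Appendix 3 form are held in the site's REDCap.
- 7.8: the investigator links the results to the clinical data after the manufacturer has returned them.

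So nothing in the plan gives the analysts ostomy status when they search for the earliest useful time. Nothing forbids it either.

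**2. Inputs.** The documents give N = 200. They give no ostomy share, no expected correlation, no alpha and no power, so 200 cannot be reproduced from stated inputs. Everything below except N is assumed.

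**3. Formula.** Let p be the ostomy share, r the correlation without an ostomy, r_s the correlation with one, and dx and dy the shifts in signal and event time in ostomy patients, in SD units. Then

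r_pooled = [(1−p)r + p·r_s + p(1−p)·dx·dy] / √{[1 + p(1−p)dx²][1 + p(1−p)dy²]}

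**4. Results with r_s = 0.**

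| r | dx | dy | p = 10% | p = 20% | p = 30% |
|---|---|---|---|---|---|
| -0.60 | 0 | 0 | -0.54 | -0.48 | -0.42 |
| -0.60 | 0 | -1 | -0.52 | -0.45 | -0.38 |
| -0.30 | 0 | -1 | -0.259 | -0.223 | -0.191 |
| -0.30 | -1 | -1 | -0.165 | -0.069 | 0.000 |
| -0.30 | +1 | -1 | -0.330 | -0.345 | -0.347 |

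Example, row 2 at p = 20%: 0.8 × (-0.60) / √(1 + 0.16) = -0.48 / 1.077 = -0.446.

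Example, last row at p = 20%: (0.8 × (-0.30) − 0.16) / 1.16 = -0.40 / 1.16 = -0.345, which is stronger than the true -0.30. The same shifts applied to r = -0.60 give (-0.48 − 0.16) / 1.16 = -0.55, which is weaker. The direction therefore depends on values that nobody has stated.

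If the correlation is the same in both groups (r_s = r = -0.30) and only event time shifts by 1 SD, the pooled values are -0.287, -0.279 and -0.273, a small change.

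**5. Prediction error.** 6.4.3.1 cites the RMS residual from a linear fit as the summary used in the earlier flatus study. In SD units the residual is √(1−r²). At r = -0.60 it is √0.64 = 0.80. At the pooled -0.48 (row 1, p = 20%) it is √0.7696 = 0.88, so the reported error would be about 10% larger.

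**6. Cost of separating.** Take a two-sided alpha of 0.05 and 80% power. The detectable |r| is tanh[(1.960 + 0.842)/√(n−3)]:

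- n = 200: 0.197
- n = 180: 0.208
- n = 160: 0.220
- n = 140: 0.235

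For a weak true correlation of -0.20, with r_s = 0, dx = 0 and dy = -1, power with all 200 pooled is 69%, 56% or 44% at p = 10%, 20% or 30%. With ostomy patients left out it is 77%, 72% or 66%. Under those assumptions the smaller, cleaner set does better.

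**The case against.** The strongest reply has four parts.

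**The plan nowhere says that it will pool.** Section 6.4.4 nominally makes every item in 6.4.3.4 a subset or covariate, and 6.4.3.1 leaves the final approach open because this is a pilot. This stands in part. Pooling follows from silence and from the data flow, so the fair charge is that no handling rule exists. A bare cross-reference to a descriptive list does not supply one.

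**Stoma output may still mark recovery.** The outcome is GI recovery, section 2.2 speaks of continuity and not of colonic transit, and the metrics cover several organs. With some stomas part of the colon remains in circuit. This also stands in part: a zero correlation in ostomy patients is an assumption and may be too pessimistic. But the anastomotic part of the stated meaning is lost when the stoma lies above the join, and the form records neither route nor stoma type.

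**The hypothesis test may survive.** At the lowest value shown for r = -0.60, which is -0.38, power with 200 patients exceeds 99%. That is correct. For a strong correlation the harm is to its estimate and to the prediction error, not to detection. Solid-meal and discharge times do not depend on route.

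**The split remains possible later,** because ostomy status is collected and results are re-linked. True, but by then the optimal time would have been chosen on the mixed data.

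A reader might go further and infer that diversion would show up as a false right/left/rectal difference. The documents do not support this. The secondary objective in 4.3 compares signal patterns, flatus time is not an input to it, and nothing in the documents says that a stoma changes the signal.

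**Conclusion.** The point holds as a gap in definition and analysis. Patients with both an anastomosis and an ostomy are eligible and expected, the two bowel-function events are recorded without route, and no rule separates these patients in the correlation. One pooled coefficient can therefore be distorted.

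The size is conditional. The figures of -0.54 to -0.42 rest on an assumed -0.60 without an ostomy, zero with one, no shift in signal or event time, and a share of 10% to 30%. The documents supply none of these. The anastomosis criterion limits the affected group to patients with both a join and a stoma, unless the looser Appendix 2 wording is what gets applied.

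A reader might infer that the bias always runs toward zero. That is not supported: the last row of the table shows inflation, and an equal correlation in both groups leaves little change. The worthwhile conclusion is that the plan should separate the groups by a field it already collects.

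**What to change.** - **Analysis (6.4.3.1 and 6.4.4).** Report the first-flatus and first-bowel-movement correlations separately by postoperative ostomy status. Make patients without a postoperative ostomy the main flatus analysis. Give the all-patient result as a sensitivity analysis, both stratified or adjusted for ostomy and simply pooled.
- **Definition (5.2.1 and 5.2.2).** Name the event in ostomy patients as first gas or first output in the appliance.
- **Form (Appendix 3).** Add a route tick-box, anus or stoma, beside each of the two dates. Ostomy status will often imply the route, but the box settles the exceptions when the event happens and avoids the telephone recall in 6.4.5.
- **Data flow (7.5 and 7.8).** Send ostomy status, under the study number, to the manufacturer's analysts before the search for the optimal time.
- **Eligibility.** Reconcile 5.3.2 with the Appendix 2 checklist on resection and anastomosis.

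The cost is a few sentences, one form item and one transferred variable. The real downside is a smaller main flatus analysis. At an assumed 20% share it has 160 of 200 patients, and the detectable |r| at 80% power rises from 0.197 to 0.220. No patient leaves the study.
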